6.3.2 Expected accrual

It is expected that 2-3 patients per month may enroll on this trial to enroll a total of 130 patients who are randomized. A total of 20 HCLv and 25 classic HCL patients are allowed who will not be randomized, making a total of 175 evaluable patients enrolled for study intervention. An accrual period of 15 years is anticipated. The accrual ceiling will be 208 to account for inevaluable participants.

7 COLLABORATIVE AGREEMENTS

7.1 COOPERATIVE RESEARCH AND DEVELOPMENT AGREEMENT (CRADA)

CRADA #02753 between Genentech and NCI was executed 11/8/2012 and amended 11/3/2017.

8 HUMAN SUBJECTS PROTECTIONS

8.1 RATIONALE FOR SUBJECT SELECTION

Both men and women from all races and ethnic groups are eligible for this trial.

8.2 PARTICIPATION OF CHILDREN:

HCL is a disease of adults, not children, and it is unlikely that any children will be diagnosed.

8.3 PARTICIPATION OF SUBJECTS UNABLE TO GIVE CONSENT

Adults unable to give consent are excluded from enrolling in the protocol. However, re-consent may be necessary and there is a possibility, though unlikely, that subjects could become decisionally impaired. For this reason and because there is a prospect of direct benefit from research participation (Section [8.4](#)), all subjects will be offered the opportunity to fill in their wishes for research and care, and assign a substitute decision maker on the “NIH Advance Directive for Health Care and Medical Research Participation” form so that another person can make decisions about their medical care in the event that they become incapacitated or cognitively impaired during the course of the study. Note: The PI or AI will contact the NIH Ability to Consent Assessment Team (ACAT) for evaluation to assess ongoing capacity of the subjects and to identify an LAR, as needed.

Please see Section [8.5.1](#) for consent procedure.

8.4 EVALUATION OF BENEFITS AND RISKS/DISCOMFORTS

Rituximab may offer improved clinical endpoints when combined with cladribine, including improved response, disease-free and overall survival. Patients may benefit by close follow-up after treatment, particularly if treatment is needed for early relapse.

If rituximab fails to eliminate MRD, it could select for cells deficient in apoptosis and render patients unresponsive to rituximab and other agents when they relapse later in their disease course. Moreover, it is possible that the risk of infection may increase with use of rituximab with cladribine.

8.4.1 Risks from Study Procedures

8.4.1.1 Blood draws

Side effects of blood draws include pain and bruising, lightheadedness, and rarely, fainting.

8.4.1.2 Urine collection

There is no physical risk involved with urine collection.

8.4.1.1 Bone marrow biopsy

Bone marrow biopsy is minimally invasive and is typically a very safe procedure. Usually hipbone is numbed with anesthesia. Using a needle, the solid and liquid portion of bone marrow is taken out. This procedure causes some pain. Very rarely, infection or bleeding may occur at the needle site.

8.4.1.2 Local anesthesia

Bone marrow biopsy may be done under local anesthesia. Potential side effects of local anesthesia include drowsiness, headaches, blurred vision, twitching muscles or shivering, continuing numbness, weakness or pins and needles sensation.

8.4.1.3 Echocardiogram

There is no physical risk involved with echocardiogram. Side effects of an echocardiogram are discomfort from the transducer being firmly placed against the chest.

8.4.1.4 Electrocardiogram

Some skin irritation can occur where the ECG/EKG electrodes are placed. The test is completely painless, and generally takes less than a minute to perform.

8.4.1.5 Stress test

A stress test is generally safe, and complications are rare. Risks of complication include hypotension, arrhythmias, or myocardial infarction.

8.4.1.6 Pulmonary function tests (PFTs)

PFTs are usually safe for most people. Risks of complication include dizziness, asthma attack, or collapsed lung.

8.4.1.7 Ultrasound

No physical risks are associated with ultrasound procedures.

8.4.1.8 Imaging

In addition to the radiation risks discussed below, CT scans may include the risks of an allergic reaction to the contrast. Participants might experience hives, itching, headache, difficulty breathing, increased heartrate and swelling.

8.4.1.9 MR Imaging

The risks of MR imaging are relatively small.

Participants undergoing gadolinium enhanced MRIs may also be at risk for kidney damage. MRIs include the additional risk of damage to hearing.

8.4.2 Risks from Radiation Exposure

On this study, patients will receive up to four CT scans (including screening). The total radiation dose for research purposes will be approximately 5.2 rem. The risk of getting cancer from the radiation exposure in this study is 0.5% and of getting a fatal cancer is 0.3%.

8.5 CONSENT PROCESS AND DOCUMENTATION

The informed consent document will be provided as a physical or electronic document to the participant or consent designee(s) as applicable for review prior to consenting. A designated study investigator will carefully explain the procedures and tests involved in this study, and the associated risks, discomforts and benefits. In order to minimize potential coercion, as much time as is needed to review the document will be given, including an opportunity to discuss it with friends, family members and/or other advisors, and to ask questions of any designated study investigator. A signed informed consent document will be obtained prior to entry onto the study.

The initial consent process as well as re-consent, when required, may take place in person or remotely (e.g., via telephone or other NIH approved remote platforms used in compliance with policy, including HRPP Policy 303) per discretion of the designated study investigator and with the agreement of the participant/consent designee(s). Whether in person or remote, the privacy of the subject will be maintained. Consenting investigators (and participant/consent designee, when in person) will be located in a private area (e.g., clinic consult room). When consent is conducted remotely, the participant/consent designee will be informed of the private nature of the discussion and will be encouraged to relocate to a more private setting if needed.

Consent will be documented with required signatures on the physical document (which includes the printout of an electronic document sent to participant) or as described below, with a manual (non-electronic) signature on the electronic document. When required, witness signature will be obtained similarly as described for the investigator and participant.

Manual (non-electronic) signature on electronic document:

When a manual signature on an electronic document is used for the documentation of consent at the NIH Clinical Center, this study will use the following to obtain the required signatures:

- Adobe platform (which is not 21 CFR Part 11 compliant); or,
- iMedConsent platform (which is 21 CFR Part 11 compliant)

During the consent process, participants and investigators will view individual copies of the approved consent document on screens at their respective locations (if remote consent); the same screen may be used when in the same location but is not required.

Both the investigator and the participant will sign the document using a finger, stylus or mouse.

Note: Refer to the CCR SOP PM-2, Obtaining and Documenting the Informed Consent Process for additional information (e.g., verification of participant identity when obtaining consent remotely) found at:

<https://ccrod.cancer.gov/confluence/pages/viewpage.action?pageId=73203825>

Optional blood and bone marrow sample testing will be performed after consenting to the investigator's companion protocol, 10C0066. If the patient refuses to have samples saved for optional testing at that time, the refusal will be documented in the medical record and in the research record.

8.5.1 Consent Process for Adults Who Lack Capacity to Consent to Research Participation

For participants addressed in Section [8.3](#), an LAR will be identified consistent with Policy 403 and informed consent obtained from the LAR, as described in Section [8.5](#).

8.5.2 Request for Waiver of Consent for Screening Activities

Prior to the subject signing the consent for this study pre-screening activities listed in Section [2.2.1](#) may be performed.

We request a waiver of consent for these activities as they involve only minimal risk to the subjects. A waiver will not adversely affect the rights and welfare of the subjects given that the activities are only intended to determine suitability for screening for participation in research protocols. These activities could not practicably be carried out without the waiver as central recruiting services, utilized in the NIH Clinical Center, perform pre-screening activities for multiple studies

and obtaining consent for each one is beyond their resources. The subjects will be provided with additional pertinent information after participation as they will be informed whether or not they are eligible to sign a consent for additional screening.

9 CORRELATIVE STUDIES FOR RESEARCH

9.1 BIOSPECIMEN COLLECTION

9.1.1 Description of data/specimens

9.1.1.1 Blood and bone marrow samples.

Note: Samples collected during the course of this study will be stored, tracked, and disposed of as specified in investigator's companion protocol, 10-C-0066, on which all subjects will be co-enrolled.

Samples collected from patients enrolled prior to Amendment W may be stored, tracked and disposed of as specified in investigator's companion protocol, 10-C-0066 if subject have been co-enrolled.

9.2 RESEARCH BEING CONDUCTED

Malignant cells may be stored to determine sensitivity to recombinant immunotoxins like BL22 or to related agents. Immunoglobulin expression is characterized to better understand origin of disease and prognostic factors. Genetic markers may be cloned to serve as sensitive indicators of minimal residual disease, and serum markers for disease may also be determined. Integrins and other factors on the malignant cells which are known to interact with the microenvironment in leukemias may be studied. PD1 expression by the malignant cells may also be studied, as well as other markers that may allow the malignant cells to suppress the immune system. ELISA assays for inflammatory cytokines, including interleukin 6 and interleukin-1 receptor antagonist, may be done on prospectively saved plasma samples.

9.3 SAMPLE STORAGE, TRACKING AND DISPOSITION

Samples will be ordered in CRIS and tracked through a Clinical Trial Data Management system. Should a CRIS screen not be available, the CRIS downtime procedures will be followed. Samples will not be sent outside NIH without appropriate approvals and/or agreements, if required.

Samples will be stored and cataloged longer than a year, in alarmed freezers at our Leidos Biomedical Research, Inc. contract lab in Frederick, MD, where neutralizing antibodies and PK samples are tested. After closure of the protocol, the samples will either be destroyed, or their storage and use will be governed by a subsequent protocol. Portions of samples which are stored at Frederick National Laboratory for Cancer Research may also be stored and tested in the LMB lab (Building 37) for longer than a year providing there is sample remaining after studies are done.

Samples sent to Amplimmune or MD Anderson will have identifiers removed and may be stored by these institutions for longer than a year before they are destroyed.

Samples at Leidos Biomedical Research, Inc. in Frederick, Maryland will be tracked in a secure electronic database and the PI will record any loss or unanticipated destruction of samples as a deviation. Reporting will be per the requirements of Section **10.2**.

10 NIH REQUIREMENTS/ DATA AND SAFETY MONITORING PLAN

10.1 DEFINITIONS

Please refer to definitions provided in Policy 801: Reporting Research Events found at: <https://irbo.nih.gov/confluence/pages/viewpage.action?pageId=36241835#Policies&Guidance-800Series-ComplianceandResearchEventReportingRequirements>.

10.2 OHSRP OFFICE OF COMPLIANCE AND TRAINING / IRB REPORTING

10.2.1 Expedited Reporting

Please refer to the reporting requirements in Policy 801: Reporting Research Events and Policy 802 Non-Compliance Human Subjects Research found at: <https://irbo.nih.gov/confluence/pages/viewpage.action?pageId=36241835#Policies&Guidance-800Series-ComplianceandResearchEventReportingRequirements>.

10.2.2 IRB Requirements for PI Reporting at Continuing Review

Please refer to the reporting requirements in Policy 801: Reporting Research Events found at: <https://irbo.nih.gov/confluence/pages/viewpage.action?pageId=36241835#Policies&Guidance-800Series-ComplianceandResearchEventReportingRequirements>.

10.3 NCI CLINICAL DIRECTOR REPORTING

Problems expeditiously reported to the OHSRP in the NIH eIRB system will also be reported to the NCI Clinical Director/designee; therefore, a separate submission for these reports is not necessary.

In addition to those reports, all deaths that occur within 30 days after receiving a research intervention should be reported via email unless they are due to progressive disease.

To report these deaths, please send an email describing the circumstances of the death to [contact] within one business day of learning of the death.

10.4 NIH REQUIRED DATA AND SAFETY MONITORING PLAN

10.4.1 Principal Investigator/Research Team

The clinical research team will meet on a weekly basis when patients are being actively treated on the trial to discuss each patient. All data will be collected in a timely manner and reviewed by the principal investigator or a lead associate investigator. Events meeting requirements for expedited reporting as described in Section **10.2.1** will be submitted within the appropriate timelines.

The principal investigator will review adverse event and response data on each patient to ensure safety and data accuracy. The principal investigator will personally conduct or supervise the investigation and provide appropriate delegation of responsibilities to other members of the research staff.

11 SAFETY REPORTING CRITERIA TO THE PHARMACEUTICAL COLLABORATORS

11.1 ADVERSE EVENT REPORTING TO GENENTECH

- In the event of an adverse event, the first concern will be for the safety of the subject. Investigators are required to report to Genentech Drug Safety any **serious adverse event**, whether **expected** or **unexpected**, regardless of causality to rituximab.
- The Sponsor-Investigator further agrees to forward reports to Genentech of serious adverse events considered to be associated with the use of rituximab.
- All events meeting these criteria will be reported for the time period beginning with any amount of exposure to rituximab through the protocol-defined follow-up period. Serious criteria, definitions, and guidance for reporting follow.
- An **adverse event (AE)** is any untoward medical occurrence in a subject participating in an investigational trial or protocol regardless of causality assessment. An adverse event can be an unfavorable and unintended sign (including an abnormal laboratory finding), symptom, syndrome or disease associated with or occurring during the use of an investigational product whether or not considered related to the investigational product.
- **Serious adverse events (SAE)** are adverse events occurring at any dose which meet one or more of the following **serious criteria**:
 - Results in **death** (i.e. the AE caused or lead to death)
 - Is **life-threatening** (i.e. the AE placed the subject at immediate risk of death; it does not apply to an AE which hypothetically might have caused the death if it were more severe)
 - Requires or prolongs inpatient **hospitalization** (i.e. the AE required at least a 24-hour inpatient hospitalization or prolonged a hospitalization beyond the expected length of stay; hospitalizations for elective medical/surgical procedures, scheduled treatments, or routine check-ups are not SAEs by this criterion)
 - Is **disabling** (i.e. the AE resulted in a substantial disruption of the subject's ability to carry out normal life functions)
 - Is a **congenital anomaly/birth defect** (i.e., an adverse outcome in a child or fetus of a subject exposed to the trial drug prior to conception or during pregnancy)
 - It does not meet any of the above serious criteria but **may jeopardize the subject** and **may require medical or surgical intervention** to prevent one of the outcomes listed above
 - SAEs include any sign, symptom or medical condition that meets any of the above criteria and emerges during rituximab treatment or during a post-treatment follow-up period that (1) was not present at the start of treatment and is not a chronic condition that is part of the patient's medical history, OR (2) was present at the start of treatment or as part of the patient's medical history but worsened in severity and/or frequency during therapy.

- **Expected** adverse events are those adverse events that are **listed** or characterized in the current Investigator Brochure.
- **Unexpected** adverse events are those **not listed** in the current Investigator Brochure or not identified. This includes adverse events for which the specificity or severity is not consistent with the description in the Investigator Brochure. For example, under this definition, hepatic necrosis would be unexpected if the Investigator Brochure only referred to elevated hepatic enzymes or hepatitis.

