- **Infectious Events:** Rituxan induced B-cell depletion in 70% to 80% of patients with NHL and was associated with decreased serum immunoglobulins in a minority of patients; the lymphopenia lasted a median of 14 days (range, 1-588 days). Infectious events occurred in 31% of patients: 19% of patients had bacterial infections, 10% had viral infections, 1% had fungal infections, and 6% were unknown infections. Serious infectious events (Grade 3 or 4), including sepsis, occurred in 2% of patients.
- **Hepatitis B Reactivation:** Hepatitis B virus (HBV) reactivation with fulminant hepatitis, hepatic failure, and death has been reported in some patients with hematologic malignancies treated with rituximab. The majority of patients received rituximab in combination with chemotherapy. The median time to the diagnosis of hepatitis was approximately four months after the initiation of rituximab and approximately one month after the last dose.
- **Other Serious Viral Infections:** The following additional serious viral infections, either new, reactivated or exacerbated, have been identified in clinical studies or postmarketing reports. The majority of patients received Rituxan in combination with chemotherapy or as part of a hematopoietic stem cell transplant. These viral infections included JC virus (progressive multifocal leukoencephalopathy [PML]), cytomegalovirus, herpes simplex virus, parvovirus B19, varicella zoster virus, West Nile virus, and hepatitis C. In some cases, the viral infections occurred up to one year following discontinuation of Rituxan and have resulted in death.

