3.4 PROTOCOL EVALUATION

3.4.1 Pre-treatment evaluation (See Section [2.4](#))

3.4.2 Evaluation during study (See Section [15.1](#))

3.4.3 Post Treatment Evaluation (Follow-up)

- Patient follow-up at least semiannually will continue by clinic visit, phone, or secure email using NIH approved system to determine disease-free and overall survival. In patients who develop progressive disease, follow up will continue by annual phone call only, to determine overall survival.
- Patients will be closely followed to determine resolution of grade IV toxicity.

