5 DATA COLLECTION AND EVALUATION

5.1 DATA COLLECTION

The PI will be responsible for overseeing entry of data into a 21 CFR Part 11-compliant data capture system provided by the NCI CCR and ensuring data accuracy, consistency and timeliness. The principal investigator, associate investigators/research nurses and/or a contracted data manager will assist with the data management efforts. Primary and final analyzed data will have identifiers so that research data can be attributed to an individual human subject participant.

Patients treated both inside and outside of NIH will require source documentation regarding dosage and timing of drug administration. For patients treated outside NIH, results of lab, radiology and pathology tests should be faxed to the PI

All adverse events, including clinically significant abnormal findings on laboratory evaluations, regardless of severity, will be followed until return to baseline or stabilization of event.

Document AEs from the first study intervention, Study Day 1, through 30 days after the end of treatment. Beyond 30 days after the last intervention, only adverse events which are serious and related to the study intervention need to be recorded.

An abnormal laboratory value will be recorded in the database as an AE **only** if the laboratory abnormality is characterized by any of the following:

- Results in discontinuation from the study
- Is associated with clinical signs or symptoms
- Requires treatment or any other therapeutic intervention
- Is associated with death or another serious adverse event, including hospitalization.
- Is judged by the Investigator to be of significant clinical impact
- If any abnormal laboratory result is considered clinically significant, the investigator will provide details about the action taken with respect to the test drug and about the patient's outcome.

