11.1.1 Reporting of Serious Adverse Events Associated with Rituximab

All serious adverse events (SAEs) regardless of causality to rituximab (this applies to both expected and unexpected events) should be recorded on a MedWatch 3500A Form and faxed to:

Genentech Drug Safety

[contact]

[contact] or [contact]

(Please use the safety reporting fax cover sheet attached to this document for your fax transmission.)

Forward all SAEs also to the IRB and PI as directed in Section **10.2**

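### Sections 5.1 and 11.1 set different rules for late serious adverse events, so late counts in the trial dataset depend on attribution and are not comparable between Arms 1 and 2

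*Combined protocol and SAP*

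**What the plan says.** Section 11.1 obliges investigators to report any SAE to the company, "whether expected or unexpected, regardless of causality to rituximab". The reporting period runs from "any amount of exposure to rituximab through the protocol-defined follow-up period". Section 11.1.1 repeats the scope ("All serious adverse events (SAEs) regardless of causality to rituximab") and adds the IRB and the principal investigator as recipients.

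Section 5.1 describes what goes into the trial's data capture system. All adverse events are documented from Study Day 1 to 30 days after treatment ends. The rule then changes: "Beyond 30 days after the last intervention, only adverse events which are serious and related to the study intervention need to be recorded".

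The follow-up period that 11.1 relies on is not defined there. The nearest description is in 3.4.3, which gives no end date: "Patient follow-up at least semiannually will continue by clinic visit, phone, or secure email". After progression, 3.4.3 reduces contact to a yearly telephone call for survival only.

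Under 11.1.3.2 the investigator decides whether an event is related. Section 5.1.1 collects dates of death for overall survival, with no attribution condition.

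**The concern.** A late SAE that the investigator judges unrelated is reportable under 11.1 but is not a required entry under 5.1. No section says that Section 11 reports are also entered in the database or checked against it. A dataset built to 5.1 as written would therefore hold late SAEs that have passed through an attribution judgement. The protocol describes no placebo, blinding or independent adjudication, so that judgement is made by people who know the treatment.

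This matters because the protocol treats late and infectious harm as an open question. Section 1.3.3 gives a possible rise in infection with the combination as one reason for randomising, and 8.4 repeats it as a risk. Section 1.2.6 says of serious viral infections that, in some cases, "the viral infections occurred up to one year following discontinuation of Rituxan and have resulted in death". Section 1.3.4 allows that the trial may lead to a recommendation of the combination as standard treatment. A reader weighing that recommendation would want late SAE counts collected in the same way in both randomised arms.

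**Working it through.** The plan gives no figure to reproduce. The check compares the two rules and then works out the recording windows.

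**The rules side by side**

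| | 5.1 | 11.1 and 11.1.1 |
|---|---|---|
| Destination | Trial database | Company, IRB, principal investigator |
| Start | First study intervention | First rituximab exposure |
| SAEs regardless of cause until | 30 days after treatment | End of follow-up (undefined) |
| Afterwards | Serious and related, as a minimum | Not stated |

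Take a serious infection at month 5 that is judged unrelated. In Arm 1 it must be reported under 11.1 but need not be recorded under 5.1. In Arm 2, before any rituximab, neither section requires it.

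**Windows, taking the day-1 course as the treatment**

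Inputs:
- cladribine on days 1 to 5 (3.2.1)
- eight weekly rituximab doses from day 1 in Arm 1 (3.2.2)
- the 30-day rule (5.1)
- primary evaluation at 24 to 28 weeks (6.1), with the midpoint taken as 26 × 7 = day 182.

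Results:
- Arm 1: last rituximab dose 1 + 7 × 7 = day 50. Recording regardless of cause ends at 50 + 30 = day 80.
- Arm 2: last cladribine dose day 5. Recording regardless of cause ends at 5 + 30 = day 35.
- Difference: 80 − 35 = 45 days more in Arm 1.
- Attribution-filtered time before the 6-month evaluation: 182 − 80 = 102 days in Arm 1 and 182 − 35 = 147 days in Arm 2.

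**What changes these figures**

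Dosing is assumed to be on schedule. Section 3.3.1 allows delays of up to 2 weeks for cladribine and up to 12 weeks for rituximab, which would move the end dates later. A delayed rituximab course would open a further window. If the end of treatment means the end of all protocol therapy, the windows cannot be fixed in advance, because delayed rituximab depends on MRD.

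**Entering the 11.1 reports alone does not restore comparability**

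If those reports were entered and nothing else changed, Arm 1 would have SAE capture regardless of cause throughout. Arm 2 would still have none from day 35 until delayed rituximab, which is 147 days up to the 6-month evaluation. A common window is needed as well.

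**The case against.** The strongest reply is that the two sections do different jobs and staff can comply with both. Section 5.1 states what must be recorded and forbids nothing, while Section 11 governs reporting to the company. For rituximab-exposed patients, 11.1.1 already produces a written report of every SAE that reaches the principal investigator and the IRB, and 10.4.1 has the principal investigator review adverse event data on each patient. Deaths are collected whatever the cause. All of this stands, and it narrows the gap to required entry in the analysable dataset. A minimum still leaves entry optional, and non-fatal SAEs have no equivalent of the death record.

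A second reply is that Section 6 plans no between-arm SAE comparison, and that 1.3.4 rests its possible recommendation on response and MRD. That is correct, so no planned analysis fails. But infection risk is a stated reason for the randomisation, and the dataset should be able to inform it.

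Three stronger readings are tempting, and the documents do not support them.
- A reader might infer that late unrelated SAEs are discarded or cannot reach the trial data. Section 5.1 does not bar them, and 11.1.1 brings those in rituximab-exposed patients to the principal investigator.
- A reader might cite myelodysplasia as a harm that falls after the window. Section 13.1.2.3 lists it as rare with cladribine but gives no time of onset.
- A reader might express the 5.1 window as a share of the follow-up that 11.1 requires. With no end of follow-up defined, any horizon is arbitrary, and delayed courses add windows that such a share would ignore.

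The viral infections in 1.2.6 are also a listed rituximab risk, and 11.1.3.2 sets a low bar for possible relatedness. They may be among the events least likely to be filtered out. They show that late serious harm is expected, not that it would be missed.

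**Conclusion.** The inconsistency is real and should be corrected. Beyond 30 days after the last intervention, 11.1 and 11.1.1 require SAEs regardless of cause in rituximab-exposed patients, while the database rule requires only those judged related. Late non-fatal SAE counts built to 5.1 therefore depend on investigator attribution.

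They are also not comparable between the randomised arms if the day-1 course is taken as the treatment and doses are on schedule: the window closes 45 days earlier in Arm 2, and 11.1 offers Arm 2 nothing before delayed rituximab. That the judgement is unblinded is inferred from the absence of any placebo or blinding; the protocol does not say so in terms.

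Neither the number of SAEs affected nor the direction of any distortion can be derived from the documents. The primary MRD endpoint is not touched.

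**What to change.** Amend 5.1 in two respects:
- Every SAE reportable under 11.1 is also entered in the trial database, with attribution kept as a data field.
- In both randomised arms, SAEs are recorded regardless of attribution from the first dose of either drug over the same stated calendar window, for example at least through the 6-month assessment.

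Then define the follow-up period that 11.1 refers to, and reconcile it with the yearly survival-only call after progression in 3.4.3, so that SAE collection is neither open-ended nor at odds with that contact schedule. Cross-refer 5.1 and 11.1 so that both work from the same list of events.

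For rituximab-exposed patients the reports must already be prepared under 11.1.1, so the added work there is data entry. The new burden is collecting SAEs judged unrelated in Arm 2 patients who have not yet received rituximab. The documents give no basis for estimating its size, but a bounded window limits it.
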